## **RESEARCH DESIGN AND METHODS**

**Study Design:** The study will be a randomized parallel group clinical trial to compare twelve weeks of AE with a control condition (stretching and balance training) in 40 participants with SCZ (20 per group).

**Description of study population:** Participants for the study will be 40 participants treated at our Atlanta VA with a diagnosis of SCZ. Diagnosis will be confirmed by chart review and by a structured diagnostic interview (Structured Clinical Interview for DSM-IV, SCID-Axis I, patient version). Inclusion/exclusion criteria will be evaluated by means of chart review and participant interview.

**Inclusion criteria:** (1) Diagnosis of SCZ; (2) male or female, ages 18-70; (3) maintained on stable doses of outpatient psychiatric medications for at least 30 days; (4) compliant with outpatient follow-up (defined as coming for at least 75% of outpatient appointments within the previous 12 months); (5) have a stable place to live; (6) access to transportation to the VA. Participants will be sedentary as defined by reporting <20 min/week of performing regular physical activity in the past month.

**Exclusion criteria:** (1) Bipolar disorder;

- Criteria to rule out participants unlikely to be able to comply with treatment schedule: (2) active substance dependence within the prior 30 days; (3) more than 2 psychiatric admissions within the prior six months
- Criteria to rule out participants unlikely to be able to benefit from treatment: (4) known HIV infection or AIDS; (5) history of traumatic brain injury; (6) seizure disorder; (7) known Alzheimer's disease or other dementia; (8) clinical history of mild cognitive impairment (MCI); (9) Parkinson's disease; (10) other current clinically significant neurological disease, (11) unstable medical condition that would be expected to interfere with fitness training; (11) significant hearing or visual impairment.

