To assess feasibility we will collect data on the numbers of SCZ participants who are potentially interested in participation, the number who screen out and for what reasons, the number of drop outs, and the reasons for their dropping out. We will also collect data on attendance and barriers to attendance. For these measures we will compute descriptive statistics. These data will inform proposals for fully powered future studies.

**Specific Aim 2:** Evaluate whether increases in cardiovascular fitness ( $VO_2\text{max}$ ) mediates cognitive improvement. We predict that the degree of estimated  $VO_2\text{max}$  improvement in the AE group will predict the degree of cognitive improvement with training.

**Statistical analysis:** We will assess potential mediator effects of  $VO_2\text{max}$  as well as potential moderator effects of age, sex, and anticholinergic load to better formulate covariates in future models. The association between potential moderators and cognitive improvement will be evaluated through use of bivariate and multiple correlations; only significant associations will be further assessed as possible moderators. The assessment of  $VO_2\text{max}$  as a potential mediator will be evaluated using partial correlation coefficients from the regression model. With a total sample size of 20 participants in the treatment group, we will be sensitive to a bivariate effect size of  $r = 0.428$  at an alpha level of 0.05 with a power of 0.80. This would allow us to detect differences of up to 18% in potential moderator variables. In a multiple regression with four predictor variables (because of issues of multicollinearity with anticipated high degrees of correlation possible between the potential moderator variables, it is doubtful that we will have a viable model with more than four predictors), we will be sensitive to an overall effect size of  $f^2 = 0.063$ . Although sensitivity is provided, we consider the analyses used in the evaluation of this pilot data to be focused on estimation of effect sizes for future studies rather than for inferential interpretation. Because of this, p-values (and criterion alpha levels) will not be corrected for multiple independent testing. We will also run an exploratory regression model with mean training hours per week.

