## Sample size determination

Sample size calculations for our primary outcome measure (MCCB) are based on several studies of AE compared to a control condition in which the effect sizes average approximately 0.5 (Dustman et al. 1984; Fabre et al. 2002; Heyn et al 2004; Hotting et al. 2012; Chapman et al. 2013). We also based estimated power on studies of cognitive remediation in SCZ, including a meta-analysis (Wykes et al. 2011) and studies of Posit Science computerized remediation (Fisher et al. 2010). The average effect size of the above studies is 0.5. With alpha set at 0.05, an effect size of 0.5 will yield a power of 0.80 for our **planned sample size of 20 completers per treatment group (with dropouts replaced)**. This sample size will be adequate to detect significant between group differences in MCCB change scores. More importantly for a pilot study, this sample size will allow us to estimate effect sizes specific to the target Veteran population with sufficient confidence to be useful in determining the sample size required for a future full Merit Review proposal (if indicated by the results of this pilot study). Participant retention will be an important issue. We estimate liberally from our prior work (cognitive remediation study) that *dropouts will be approximately 25%, so we will need to recruit 53 subjects in order to obtain the 40 completers needed for analysis.*

**Roles of members of the research team.** Please see delineation of roles in Budget Justification.

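### Twenty completers per arm cannot estimate the exercise effect precisely enough to set the Merit sample size: the 95% interval is about ±0.63 SD of the analysed score

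*Combined protocol and SAP*

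**What the plan says.** The section on sample size determination plans for a "planned sample size of 20 completers per treatment group (with dropouts replaced") and takes its expected effect from earlier exercise and cognitive remediation studies: "The average effect size of the above studies is 0.5". After a power statement it turns to what it ranks as more important for a pilot, namely that "this sample size will allow us to estimate effect sizes specific to the target Veteran population with sufficient confidence to be useful" for sizing a full Merit Review proposal, if the results point to one. It gives no confidence interval, no target half-width and no rule for turning the estimate into a sample size.

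The analysis text for Specific Aim 2 describes the pilot analyses in the same spirit, as "focused on estimation of effect sizes for future studies rather than for inferential interpretation".

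Under Specific Aim 1 the plan also collects feasibility data: numbers interested, screen failures, drop-outs with reasons, and attendance. Of these it says "These data will inform proposals for fully powered future studies". That sentence concerns recruitment and retention, not effect size. The plan does not mention the residual SD or the baseline to 12-week correlation of the MCCB as planning quantities.

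**The concern.** The sentence claims a level of precision, and the claim can be checked. A required sample size varies with the inverse square of the standardised effect, so modest error in the effect becomes large error in the size. If the pilot estimate were carried into the Merit calculation, a high estimate would give an underpowered trial, and a low one would give an infeasible trial or end work on an intervention that may help. The pilot's own conduct and its primary analysis are not affected. What is at stake is how its result is used.

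**Working it through.** **Inputs**
- 20 completers per arm, expected effect 0.5, alpha 0.05, power 0.80: section on sample size determination.
- Equal allocation: study design paragraph, "in 40 participants with SCZ (20 per group").
- Analysis: ANCOVA of change with baseline, age, sex and anticholinergic load (statistical analysis plan, Specific Aim 1).
- Assumptions: two-sided test, as sidedness is not stated; pre-post correlation of the MCCB, which the documents do not give, varied from 0.5 to 0.9.

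**1. The plan's own figure.** The plan states that "an effect size of 0.5 will yield a power of 0.80". For a two-sample t-test the noncentrality is d√(n/2) = 0.5 × √10 = 1.58 on 38 df. Power is 0.34 two-sided and 0.46 one-sided, so 0.80 is not reproduced. The Aim 1 sensitivity, f = 0.456 or d = 2f = 0.912, does give 0.80. The power discrepancy is a separate matter. It is relevant here only because it shows that 20 per arm resolves effects near 0.9, not 0.5.

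**2. Precision of the standardised difference.** SE(d) = √(2/n + d²/(4n)) = √(0.1 + 0.25/80) = 0.321. The half-width is 1.96 × 0.321 = 0.629. The exact noncentral-t interval at an observed d of 0.5 is -0.13 to 1.13.

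**3. Implied Merit size.** For 80% power, n per arm ≈ 2(1.96 + 0.842)²/d² = 15.7/d².
- d = 0.5: 62.8, so 63 (64 with the t distribution).
- d = 1.13: 12.3, so 13 (14 with t).
- d = -0.13: no finite size, because the sign is reversed.

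**4. Spread over repeated pilots if the true d is 0.5.** The quartiles of the estimate are about 0.29 and 0.73, which imply about 190 and 31 per arm. In 200,000 simulated pilots, the size implied by the point estimate was within 25% of the correct 63 in 16%. It was under half of it in 26%, and over double or undefined in 32%.

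**5. Baseline-SD units with ANCOVA.** With pre-post correlation r, the residual SD is s = √(1 - r²) in baseline-SD units. The half-width is 1.96 × s × √(2/20), and n per arm is 15.7(s/d)².

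| r (assumed) | s | Half-width | n per arm at 0.5 | n per arm at lower / upper limit |
|---|---|---|---|---|
| 0.5 | 0.866 | 0.54 | 48 | none / 11 |
| 0.7 | 0.714 | 0.44 | 33 | 2,433 / 10 |
| 0.85 | 0.527 | 0.33 | 18 | 145 / 7 |
| 0.9 | 0.436 | 0.27 | 12 | 57 / 6 |

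At r = 0.85 the limits still differ by a factor of about 20 (145/7).

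**6. The plan's one numerical precision statement.** Specific Aim 3 expects descriptive estimates within 0.20 SD with 95% confidence. Applied to a difference between arms at d = 0.5, that needs 2(1.96/0.20)² × (1 + 0.25/8) ≈ 198 per arm. Even a single mean has a half-width of 1.96/√20 = 0.44 SD for one arm, or 1.96/√40 = 0.31 SD for both arms pooled. It therefore gives no support to the claim in the sample size section.

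**The case against.** The strongest reply is that the plan claims only usefulness. It does not say that the point estimate alone will fix the Merit size, and a wide interval can still inform planning alongside the published effects that the plan cites. That stands, so it would be too strong to call the resulting size arbitrary. But the plan states neither how wide the interval will be nor how the estimate will be used, so a reader cannot tell that it is too wide to settle the size.

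A second reply is that ±0.63 depends on the metric and that baseline adjustment does better. This is correct in baseline-SD units, as step 5 shows, and the metric should be named. It does not rescue the claim. The Merit size depends on the effect relative to the SD of the analysed score, and even at r = 0.9 the implied size runs from 6 to 57 per arm.

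Two stronger readings are tempting, and the documents support neither.
- A reader might infer that effect size is the only planning use of the pilot. The feasibility text under Specific Aim 1 already collects drop-out and attendance to inform future studies.
- A reader might infer that Merit will follow only a significant pilot, so that the estimate carried forward is inflated. The plan makes Merit conditional on the results but names no significance criterion, and the Aim 2 text disclaims inferential interpretation.

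**Conclusion.** The point holds: the stated precision is not a property of 20 completers per arm. With the difference standardised by the SD of the analysed score, the half-width is about 0.63. An observed 0.5 is then compatible with a Merit trial of 14 per arm or with none of any finite size. If the true effect is 0.5, the correct size is 64 per arm and the middle half of pilots would suggest about 190 down to 31. These figures assume a two-sided 0.05 test and 80% power for Merit. They do not depend on a value for the pre-post correlation. Expressing the effect in baseline-SD units does, and it narrows the interval without changing the conclusion over correlations of 0.5 to 0.9.

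This does not make the pilot too small for its other purposes, and it is not a case for enrolling more participants. It should be corrected because the claim concerns the purpose that the plan itself ranks higher, and the remedy is cheap.

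**What to change.** Replace the sentence in the section on sample size determination with three statements:

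1. With 20 completers per arm, the expected 95% half-width for the AE minus CONT difference is about 0.63 SD of the analysed score. If baseline-SD units are preferred, give the half-width with the assumed pre-post correlation.
2. The effect estimate will be reported with its 95% interval and will not by itself set the Merit sample size.
3. The Merit size will be based on a worthwhile MCCB composite difference stated in advance, together with the pilot's residual SD, baseline to 12-week correlation and drop-out.

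The sponsor must choose the worthwhile difference. Drop-out and attendance are already collected for planning under Specific Aim 1. The residual SD and correlation come from the baseline and 12-week MCCB scores already scheduled, so no new data are needed.

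The cost is wording in the protocol and analysis plan. The one real downside is that the pilot can no longer be presented as supplying the Merit effect size.

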## Description of relevance to VA

The deficits in function seen in so many of our VA SCZ patients are generally a life-long condition: thus the disabilities with which patients struggle require lifelong treatment from the VA. Improvements in cognition and everyday functioning are highly resistant to currently available treatments. Hence this proposal is highly relevant to the VA mission of rehabilitation and improving our patients' lives. Should our hypotheses be borne out in this study and in a full Merit study, our results will provide impetus to make AE part of the standard of care for SCZ, thereby leading to very real and crucially important gains for our patients.

## Potential challenges to completing the work, and how we will address them

**(a) Recruitment and retention** is always a potential issue. Please see details about our methods for recruitment and excellent track record in **section 4, Human Subjects, subsection 2a, Recruitment**.

**(b) Retaining participants** throughout the intervention will be crucial. We do not have current funds to gather pilot data on AE in SCZ to provide retention statistics for the proposed design, but our retention in AE in non-psychiatric participants in [name] lab is 82.5%, and we have retained 83% of participants in our eCaesar study, a study that lasts twice as long. The literature on AE in SCZ demonstrates the feasibility of this approach. [name] (the trainer for the eCaesar study) will be the chief staff member to supervise the training. Our participants form an excellent therapeutic alliance with [name], who has experience in retaining participants for up to a year in prior studies in our lab. See further comments on recruitment/retention in **section 4, Human Subjects, subsection 2a, Recruitment**.

**(c) Potential inability of SCZ participants to tolerate AE.** [name] has an excellent record of retention in his AE studies. Poor adherence is also a potential challenge. Common causes of poor adherence include vacations, spouse care, fatigue, and fluctuations in motivation. For all study arms, we will use a social problem solving model approach in dealing with individual adherence problems. Our team has successfully applied this problem-solving approach to promoting continued adherence in a number of our previous studies.

## 1. RISKS TO SUBJECTS

### a. Human Subject Involvement and Characteristics:

Inclusion/exclusion criteria will be assessed for each participant by means of computerized chart review as well as participant interview and, where applicable, discussion with the participants' VA clinician.

*i. Participants with SCZ.* We will recruit 40 male and female participants with SCZ, aged 18-70. A diagnosis of SCZ, any subtype, will be confirmed by SCID. Inclusion criteria will be: (1) Diagnosis of SCZ; (2) male or female, ages 18-70; (3) maintained on stable doses of outpatient psychiatric medications for at least 30 days; (4) compliant with outpatient follow-up (defined as coming for at least 75% of outpatient appointments within the previous 12 months); (5) must have a stable place to live; (6) access to transportation to the VA. The participants will receive a psychiatric and medical history and be excluded if they have: (1) Bipolar disorder; (2) active substance dependence within the prior 30 days; (3) more than 2 psychiatry admissions within the prior six months, (4) known HIV infection or AIDS; (5) history of traumatic brain injury; (6) seizure disorder; (7) known Alzheimer's Disease or other dementia; (8) clinical history of mild cognitive impairment (MCI); (9) Parkinson's Disease; (10) unstable medical condition that would be expected to impair attention; (11) hearing impairment; (12) visual impairment (worse than corrected 20/40 by eye chart screening).

### b. Sources of Research Material:

Research data will be collected solely for purposes of research unless otherwise specified. The research data obtained from human participants in this protocol will be as follows:

*i. Clinical information* obtained by medical history and psychiatric interview, symptom ratings, and cognitive testing.

*ii. Clinical information* obtained by chart review of the participants' clinical records to help in clarifying diagnostic and course information.

*iii. Urine for toxicology.* Urine samples from all participants will be tested for the presence of street drugs or abuse. This data will be collected solely for research purposes.

*iv. Results of V02max assessment and performance during AE training.* These data will be collected solely for research purposes.

*v. Results of cognitive and functional performance testing.* This will be done as part of the research protocol.

### c. Potential Risks:

All risks described are research risks. No procedures done in this project will be done as part of the participants' clinical care.

*i. Risk of obtaining clinical information by interview, ratings, and chart review.* The risks here involve potential loss of confidentiality, and emotional upset if information gathered is of a highly emotionally charged nature.

*ii. Risk of obtaining clinical information by chart review.* The only risk regards potential loss of confidentiality.

*iii. Urine for toxicology.* The only risk regards potential loss of confidentiality.

*iv. Risk of V02max assessment and performance during AE training.* The risk is of fatigue and shortness of breath, increases in heart rate and blood pressure. There is a minimal risk of a cardiac event.

*v. Risk associated with cognitive and functional performance testing.* The only risks are of mild frustration.

## 2. ADEQUACY OF PROTECTION FROM RISK

### a. Recruitment and Informed Consent:

*i. Recruitment:* Schizophrenia participants will be recruited from the clinical population of the Atlanta Veterans Affairs Medical Center. Clinical psychiatric facilities at the Atlanta VA Medical Center include a 40-bed admitting ward. There are approximately 1500 admissions per year, with roughly 30% diagnosed as having SCZ. [name] is an attending on this ward, and is therefore personally familiar with the admissions to the inpatient service. Because the clinical population at the Atlanta VA is very large, there will be ample participants to recruit for this project. In fact, the total number of unique Veteran patients treated in our outpatient Mental Health clinics increased 10% in the past year and totaled 18,937 in 2011 (Northeast Program Evaluation Center data). Approximately 30% of these outpatients have SCZ (i.e. approximately 5700). [name] works within a clinical team integrating inpatient and outpatient mental health staff and hence has ready access to recruit schizophrenia patients in the outpatient service. Additionally, the psychiatry

department at the Emory University is very active in research and has an extensive research infrastructure to aid in the recruitment of research participants.

In order to conduct recruitment for studies in the [name] lab, we have set up the following specific procedures. With Emory IRB and VA R&D Committee approval, we have obtained a list of all patients with schizophrenia in the Atlanta VA. On a monthly basis we are able to pull all appointments in the Mental Health Clinic. For instance, in a recent month [name] pulled appointments in our clinics for 670 unique VA patients with SCZ. Using a set of relational databases we are able to ascertain which of these patients with upcoming appointments have been diagnosed with SCZ. We give to each clinician a list of their patients with SCZ who are scheduled to come in that week (targeting a subset of clinicians each week). The clinicians then mention the study to appropriate patients during the appointment. If the patient is willing to speak with our research team directly, the clinician calls our lab to come down and meet with the patient after their appointment and, if they are willing, schedule a screening appointment with study staff. The intervention will be demanding of the participants' time and hence **retention will be an important issue**. Retention will be enhanced by modest participant payments to cover their travel expense (\$30 per week). Transportation issues have the potential to limit participant participation. When possible, they will be helped to access transportation by the VA or the Disabled American Veterans (DAV) van system if needed. Additionally, we are able to provide a letter stating that our participants are receiving treatment for a serious mental illness. They can bring this letter to an Atlanta subway station and receive half-price passes to ride Atlanta trains and buses. Additionally, our VA is offering a growing network of shuttle buses that are free. **These transportation options have helped our participants remain on schedule for their training sessions in the eCaesar trial and we anticipate that these same options will help recruit and retain participants for this proposed study.**

*ii. Consent procedures:* This study will not be initiated until the protocol and consent form have been fully approved by the appropriate institutional review boards of Emory University School of Medicine and the Atlanta VAMC. Only participants who have given their written informed consent will take part in this study. Written informed consent will be obtained by [name] or the research staff. Participants who have been declared incompetent will be included only if they have volunteered for the study, they have signed assent, and their conservator/guardian has signed informed consent.

All volunteers will be asked to sign consent after reading the VA consent form (10-1086), discussing the study, and being given a chance to ask questions. They will be informed that they are being asked to participate in a research study. Prior to signing informed consent, the participants will have the following elements of the consent form explained to them: the fact that participation is wholly voluntary, purpose of the study, procedures involved in the study, potential risks of the study, measures taken to minimize risks, potential benefits of the study, participant reimbursement for time and travel to participate, whom they can call (and phone numbers) if they feel they have been injured by participation or if they feel their rights have been infringed. They will be asked to read the consent form, and encouraged to ask questions or discuss any pertinent issues. They will be told that declining to serve as a participant in this study will not influence or compromise the quality of their care at the Atlanta VAMC (if they are Veterans and eligible for treatment at the VA). After participants have signed VA form 10-1086, a copy of their signed consent will be made and given to them. In accord with requirements at our VA, a copy of the consent form will be scanned into the participants' electronic clinical chart, and a note documenting the consent procedure will be entered into the electronic clinical chart. Participants will also be asked to sign a HIPAA consent, and the terms of this document will be explained to them prior to signing.

